5.4.3 Vital Signs

Vital signs assessments will be performed at Screening, at Baseline (pre and post infusion) and prior to dosing at each of the monthly infusions (Visit 4 [“Month 1”], Visit 5 [“Month 2”], Visit 6 [“Month 3”] [also post infusion], Visit 7 [“Month 4”], and Visit 8 [“Month 5”]) and at the final visit (Visit 9 [“Month 6”] or at early discontinuation) during the initial treatment period. For subjects

continuing in the extension treatment period, vital signs assessments will be performed pre and post infusion at Visit 9 (“Month 6”) and Visit 12 (“Month 9”), prior to dosing at each of the other monthly infusions (Visit 10 [“Month 7”], Visit 11 [“Month 8”], Visit 13 [“Month 10”], and Visit 14 [“Month 11”]) and at the final visit (Visit 15 [“Month 12”] or at early discontinuation).

Vital signs include body weight, temperature, pulse, systolic and diastolic blood pressure, and respiratory rate. Height will be measured at Screening and used along with body weight to calculate Body Mass Index (BMI). Pulse and blood pressure will be measured after the subject has been in the supine position for at least 5 minutes. At Day 0, prior to dosing, measurements of blood pressure and pulse (supine) will be repeated 3 times, at least 10 minutes apart, and the values will be averaged to obtain the baseline values.

The absolute values of the vital signs data will be summarized by treatment period at each visit using the summary statistics for continuous variables according to the treatment received during the period.

Change from baseline to each post-baseline visit will be calculated for each of the vital signs and the change from baseline data summarized by treatment period at each post-baseline visit using the summary statistics for continuous variables according to the treatment received during the period. The number and percentage of subjects at each visit with the abnormalities in Table 6 will be summarized:

Table 6. Vital Sign Abnormalities

Parameter	Unit	Category 1	Category 2
Systolic Blood Pressure	mmHg	Value ≤ 90 and ≥ 20 Decrease	Value ≥ 180 and ≥ 20 Increase
Diastolic Blood Pressure	mmHg	Value ≤ 50 and ≥ 15 Decrease	Value ≥ 105 and ≥ 15 Increase
Sitting Pulse Rate	bpm	Value ≤ 50 and ≥ 15 Decrease	Value ≥ 120 and ≥ 15 Increase
Respiration Rate	breaths/ minute	< 12	> 25
Temperature	C	NA	Value ≥ 38.3 and ≥ 1.1 Increase
Weight	kg	$\geq 7\%$ Decrease	$\geq 7\%$ Increase

Summaries will be repeated to reflect the use of Baseline 1 and Baseline 2, as defined in [Section 5.4.2](#).

5.4.4 12-Lead Electrocardiogram (ECG)

All subjects will have a standard 12-lead ECG performed at Screening (at any time within the 30-day screening period), pre-dose on Day 0 (**optional**; to be performed only to follow up on a clinically significant vital signs abnormality or cardiovascular AE noted at Screening), on Visit 6 (“Month 3”), and at the final visit (Visit 9 [“Month 6”] or at early discontinuation) during the initial treatment period. For subjects continuing in the extension treatment period, ECG evaluations will be done on Visit 12 (“Month 9”) and at the final visit (Visit 15 [“Month 12”] or at early discontinuation).

If clinically significant abnormalities are found, the subject’s ECG is to be repeated at regular intervals until it returns to normal.

All ECG parameters collected at different visits will be summarized by treatment period according to the treatment received during the period. Shift tables will be provided for clinically significant abnormalities and a categorical analysis evaluating QTc outliers will be performed. Summaries will be repeated to reflect the use of Baseline 1 and Baseline 2, as defined in [Section 5.4.2](#). ECG data will also be listed.

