- t) RBC osmotic resistance to be measured on a blood sample taken at screening and on a sample from the EryKit_01 bowl at the end of the process in selected centers only.
- u) Upon completion of the EDS process, the remaining sample in the satellite sample bag or, if this is not available, a sample collected from another EDS-EP sampling point, will be used for determination of DSP content and CBC.
- v) Patients meeting all selection criteria at Baseline will be randomized (1:1:1) to one of the three treatment groups.
- w) Blood sample for serum creatinine measurement to be taken before infusion.
- x) Vital signs to include height and weight measurements in triplicate at screening, baseline and each monthly visit (pre-dose).
- y) Month 12 (Visit 15; Endpoint) evaluations should be performed for all patients that complete the Extension Treatment Period, as well as patients that discontinue prematurely.
- z) The monthly infusions should be performed every 21-28 days. A window of ± 7 days will be permitted on the Day 15 visit and of + 10 days on each of the scheduled monthly post-baseline visits (Months 1 - 12). However, no EDS-EP infusion should be performed less than 21 days after the previous infusion. The window between an infusion and the subsequent one should be kept as regular as possible throughout the study, avoiding fluctuations in administration windows. The date of an infusion is not bound to the date of the initial treatment but to the date of the previous IMP administration
- aa) 1 mL blood collected, after blood diversion, for aerobic culture, before EDS process (see "Revised Study Procedures on Sterility Testing for Study IEDAT-02-2015 (ATTeST)"; [Appendix 13](#)). Moreover, a sample of the EDS-EP (approximately 1 ml per inoculum for a total of 2 mL) will be collected from the satellite sample bag, to perform a culture-based sterility test. A 1-mL sterile sample of the EDS-EP will be stored under refrigeration as a "Retention Sample".

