13.2 Vital Signs

Vital signs assessments will be performed as specified on the Schedule of Visits and Assessments and will include body weight, temperature (orally or tympanic, according to the specific medical practice of the Center), pulse, systolic and diastolic blood pressure, and respiratory rate. Height will be measured by a stadiometer in triplicate at Screening and every subsequent visit, and used along with body weight (also measured in triplicate) to calculate Body Mass Index (BMI). Pulse and blood pressure will be measured after the patient has been in the supine position for at least 5 minutes. At Day 0/1, prior to dosing, measurements of blood pressure and pulse (supine) will be repeated 3 times, at least 10 minutes apart, and the values will be averaged to obtain the baseline values.

If a change of *clinical relevance* from pre-dose to post-dose is observed, the vital signs assessment should be repeated as often as needed, at the discretion of the Investigator. Guidelines for clinically notable vital signs values are provided in [Appendix 4](#). Findings should be documented on the Vital Signs section of the Case Report Form.

Version 1.0, 09May2015; Version 2.1, 16Nov2015; Version 3.0 (Amend. 1), 01Feb2016; Version 3.1 (Amend. 2), 28Apr2016; Version 3.2 (Amend. 3), 25May2016; Version 4.0 (Amend. 4), 29Nov2016; Version 5.0 (Amend. 5, Site-specific), 20Sep2017; Version 6.0 (Amend. 6), 29Sep2017; Version 7.1 (Amend. 7.1), Final 13 March 2018, Version 8.0 (Amend. 8.0), Final 23 April 2018; Version 10.0 (Amend. 10), Final 16 April 2019; Version 11.0 (Amend. 11), Final 24 Jun 2020

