4. DEFINITIONS AND DERIVED VARIABLES

Study Day

Study Day 1 will be defined as the date of the start of the first infusion of study drug. Per CDISC guidelines, Study Day -1 will be day immediately preceding Study Day 1, and negative study days will be measured backwards from Study Day -1 (that is, Study Days -2, -3, -4, etc). There will be no Study Day 0 per CDISC guidelines, thus Study Day -1 will correspond to “Study Day 0” as mentioned in the protocol.

Age

Age will be calculated using the date of birth (DOB) and the date of randomization and will be presented in data displays as an integer using the integer (“int”) function in SAS. In the database, age will be given with two decimals.

$$\text{Age} = (\text{DOB} - \text{Date of Randomization}) / 365.25$$

Body Mass Index (BMI)

BMI will be calculated using weight in kg and height in m.

$$\text{BMI} = \text{Weight (Kg)} / \text{Height (m)}^2$$

The International Cooperative Ataxia Rating Scale (ICARS)

The International Cooperative Ataxia Rating Scale (Trouillas, 1997), the most frequently used clinician (neurologist) rated measure in patients with ataxias, was developed by a Committee of the

World Federation of Neurology to help standardize common manifestations of syndromes that lead to cerebellar dysfunction. The ICARS is a 100-point, semi-quantitative scale offering a compartmentalized quantification of the following 4 sub-scores: Posture and Gait Disturbances (34 points), Kinetic Functions (52 points), Speech Disorders (8 points), and Oculomotor Disorders (6 points).

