5. STATISTICAL METHODOLOGY

5.1 Statistical and Analytical Issues

5.1.1 Statistical Methods

All eCRF data collected will be presented within data listings. The data listings will be sorted by treatment group, subject screening number, and visit. Any data collected on subjects that were screened but subsequently not randomized, will be presented within a non-randomized group.

The date format for all presentations will be 'ddmmyyyy'.

The treatment labels for all tables, figures, and listings will be:

- **Group 1, Low Dose:** EDS-EP ~5-10 mg
- **Group 2, High Dose:** EDS-EP ~14-22 mg

- **Group 3:** Placebo

All statistical methods will be based on the International Conference on Harmonization (ICH)-E9 Guidance for Industry "Statistical Principles for Clinical Trials".

Any changes concerning the statistical analysis will be documented in an amendment to the statistical analysis plan, and/or will be described in the CSR.

If any of the assumptions underlying the formal statistical methods proposed are violated during the analysis on the final data, an alternative, more appropriate, statistical method will be used and any changes will be documented in the statistical methods section of the clinical study report (CSR), including the rationale for use.

All data will be summarized by treatment group. In addition, where appropriate, a total column will be included to summarize all subjects. Where appropriate, data will be summarized by visit in addition to treatment group.

The three treatment groups will be compared for baseline/screening demographic data (i.e., age, gender, ethnicity, and race), region, and medical history data. Demographic and historical data will be assessed for potential differences between treatment groups by means of descriptive statistics. Demographic and baseline data will be presented using the FAS and Safety Population.

P-values will be rounded to four decimal places. P-values less than 0.0001 will be reported as "<0.0001" in tables. All statistical analyses will be performed using SAS® software version 9.4 or higher (Copyright, SAS Institute Inc. SAS and all other SAS Institute Inc. product or service names are registered trademarks or trademarks of SAS Institute, Inc., Cary, North Carolina, USA).

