5.4.8 Tanner Staging

The number and percentage of safety population subjects at each Tanner stage will be summarized treatment period and by visit according to treatment received during the period. Summaries will be repeated to reflect the use of Baseline 1 and Baseline 2, as defined in [Section 5.4.2](#).

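### SAP 5.4.3 names only Screening height for BMI, against the protocol's height at every monthly visit, and specifies no summary of measured height or its change

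*SAP*

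**What the plan says.** On when height is measured, the two documents differ.

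- Protocol 13.2: "Height will be measured by a stadiometer in triplicate at Screening and every subsequent visit, and used along with body weight" to obtain BMI.
- Protocol 11.3, footnote x to the schedule: "Vital signs to include height and weight measurements in triplicate at screening, baseline and each monthly visit (pre-dose").
- SAP 5.4.3: "Height will be measured at Screening and used along with body weight to calculate Body Mass Index (BMI"). No later height is mentioned.

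On what is derived and summarised:

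- SAP 4 gives the formula, weight over height squared, with the words "BMI will be calculated using weight in kg and height in m". It does not say which visit supplies the height.
- SAP 5.4.3 lists its parameters: "Vital signs include body weight, temperature, pulse, systolic and diastolic blood pressure, and respiratory rate". The by-visit and change-from-baseline summaries follow from that list. Table 6 has a row for weight but none for height or BMI.
- SAP 5.2.3 omits height, weight and BMI from the baseline characteristics. Protocol 16.2.3 includes all three.
- SAP 5.4.1 names stunted growth and weight gain among the potentially steroid-related events, and SAP 5.4.8 tabulates Tanner stage by period and visit.
- SAP 5.10, which records departures from the protocol, says nothing about height.

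**The concern.** The trial gives monthly dexamethasone for about a year to patients aged 6 and over, many of whom are still growing, and the SAP itself treats stunted growth as a possible steroid effect. The protocol collects the direct measurement, a triplicate stadiometer height every month, yet the SAP text plans no between-arm display of it.

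What is planned does not replace it. An adverse-event category records only what someone reports. Tanner staging records pubertal stage and, under protocol 13.9, leaves out post-menarchal females and males who have completed puberty. Table 6 flags a weight gain of 7% or more, but without height the reader cannot separate ordinary growth from steroid weight gain.

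There is a second risk. A programmer who follows SAP 5.4.3 literally and derives BMI after Screening would divide a current weight by an old height.

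**Working it through.** There is no plan figure to reproduce. The check has two parts: where height and BMI appear in the SAP, and how large the BMI error would be if Screening height were carried forward.

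**1. Where height and BMI appear**

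| Place | Height | BMI |
|---|---|---|
| Protocol 13.2 and footnote x | Screening and each monthly visit | from that height and weight |
| Protocol 16.2.3 (baseline) | yes | yes |
| SAP 4 (derivations) | visit not fixed | formula only |
| SAP 5.2.3 (baseline) | no | no |
| SAP 5.4.3 text | Screening named | derivation mentioned |
| SAP 5.4.3 parameter list and Table 6 | no | no |
| SAP 6.3 table titles | not named | not named |
| SAP 5.10 (declared changes) | no | no |

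The conflict on timing is undeclared, and no SAP text commits to a summary of height, change in height, or BMI at any visit.

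**2. Size of the error if Screening height were carried forward**

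With BMI = W/H², current weight and Screening height H₀, the relative overstatement at time t is (H_t/H₀)² − 1. Weight cancels. The documents give no growth rate, so growth is an assumption. Month 6 is taken as half a year's growth and Month 12 as a full year's.

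For an assumed height of 1.2-1.4 m and growth of 5-6 cm/year, the extremes are:

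- 1.40 m, 5 cm/year: Month 6 (1.425/1.40)² − 1 = 3.6%; Month 12 (1.45/1.40)² − 1 = 7.3%.
- 1.20 m, 6 cm/year: Month 6 (1.23/1.20)² − 1 = 5.1%; Month 12 (1.26/1.20)² − 1 = 10.3%.

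As a check against the documents, the Phase II means in protocol 7.1.3.1 (29.1 kg, BMI 15.6) imply a height of about √(29.1/15.6) = 1.366 m. This is a ratio of means, so approximate.

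| Assumed growth, cm/year | Month 6 | Month 12 |
|---|---|---|
| 0 | 0% | 0% |
| 2 | 1.47% | 2.95% |
| 4 | 2.95% | 5.94% |
| 6 | 4.44% | 8.98% |
| 8 | 5.94% | 12.06% |

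Over starting heights of 1.10 to 1.50 m and growth of 2 to 8 cm/year, the range is 1.34% to 7.40% at Month 6 and 2.68% to 15.07% at Month 12.

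**3. What fixed-height BMI would miss between arms**

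Take two patients, both 1.366 m at Screening and 29.1 kg throughout, one growing 4 and the other 6 cm/year (assumed).

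- Month 6: heights differ by 1.0 cm; same-visit BMI differs by 0.22 kg/m².
- Month 12: heights differ by 2.0 cm; same-visit BMI is 14.72 against 14.31, a difference of 0.41 kg/m².
- Screening-height BMI is 15.6 for both at both visits, a difference of zero.

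**The case against.** The strongest case on the other side has four parts.

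- **BMI bias.** A reader might infer that BMI will be wrong at every visit after Screening. The documents do not support that. SAP 5.4.3 does not say that Screening height is the only one used, the formula in SAP 4 fixes no visit, and no SAP output names a post-baseline BMI. If BMI is derived only at Screening, nothing is overstated and the defect is an omission. This objection stands, so the bias is conditional.
- **Lost data.** A reader might infer that the later heights are discarded. They are not: "All eCRF data collected will be presented within data listings". The SAP also serves protocol Version 11.0, whose footnote x counts height as a vital sign, and SAP 6 puts the mock tables in a separate document. A height row in Tables 14.3.10.x is therefore possible, but nothing in the SAP text requires one.
- **Growth left unanalysed.** That also goes too far. The stunted-growth event category is summarised, and so is pubertal stage: "The number and percentage of safety population subjects at each Tanner stage will be summarized". The accurate statement is that no numerical summary of measured height is specified.
- **Limits of the remedy.** Same-visit BMI mixes height with weight gain and is not a growth measure. Raw height change is hard to read across ages 6 to adult. After Month 6, placebo switching leaves only 20 planned non-switch placebo subjects by the last period (SAP Table 5), and SAP 5.4 makes the safety analysis descriptive. These points shape the fix but do not remove the need for it.

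**Conclusion.** The point holds as an undeclared conflict plus an omission. SAP 5.4.3 names Screening height for BMI where the protocol has height at every monthly visit, and it specifies no summary of measured height or change in height. Growth is left to a reported adverse-event category and Tanner stage, neither of which measures height.

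The BMI error is conditional on a post-baseline BMI being derived from Screening height. It would then be an overstatement of about 3.6-5.1% at Month 6 and 7.3-10.3% at Month 12, under the assumed 1.2-1.4 m and 5-6 cm/year. It would be zero for patients who have stopped growing; the trial has no upper age limit, so such patients may be enrolled. The documents do not show that this error will occur, and they give no growth rate from which to fix its size.

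The matter is confined to descriptive safety reporting. The primary endpoint, alpha and power are unaffected.

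**What to change.** 1. In SAP 5.4.3 and the BMI definition in SAP 4, use height from the same visit as weight, taking the mean of the triplicate readings, in line with protocol 13.2 and footnote x.
2. Add height, change in height and BMI to Tables 14.3.10.x by visit and treatment, preferably also standardised for age and sex. Make Month 6 the main time point, since it closes the fully placebo-controlled period. Present later visits by treatment received, under both Baseline 1 and Baseline 2 as defined in SAP 5.4.2, because of the placebo switching.
3. Restore height, weight and BMI to the baseline table in SAP 5.2.3, as protocol 16.2.3 states.
4. If the sponsor does intend Screening height only, declare and justify it in SAP 5.10.

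The protocol already collects the data. The cost is SAP wording, one derivation and a few table rows; standardised scores would also need a named reference.

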5.4.5 Columbia Suicide Severity Rating Scale

The Columbia Suicide Severity Rating Scale, or C-SSRS, is a suicidal ideation rating scale created by researchers at Columbia University ([Posner, 2011](#)). It rates an individual's degree of suicidal ideation on a scale, ranging from "wish to be dead" to "active suicidal ideation with specific plan and intent." At each visit, subjects will be assigned an ideation severity score of 0 (no ideation present) to 5 (active ideation with plan and intent), per scoring instructions (Columbia University).

The scale identifies behaviors which may be indicative of an individual's intent to commit suicide. An individual exhibiting even a single behavior identified by the scale was 8 to 10 times more likely to commit suicide.

Summarization of results will be performed by treatment period separately at each visit, according to the treatment received during the period. Summaries will be repeated to reflect the use of Baseline 1 and Baseline 2, as defined in [Section 5.4.2](#).

For the FAS only, the mean ideation severity score will be plotted over time during the initial treatment period with separate trend lines for each of the three treatment groups. This type of plot will be repeated for mean ideation severity score and mean change from baseline in ideation severity score for each treatment period, with separate trend lines for the treatments during the period. Separate sets of plots will be prepared using each type of baseline (Baseline 1 and Baseline 2).

5.4.6 Laboratory Parameters

Standard Laboratory Evaluations

Hematology, clinical chemistry, and urinalysis will be performed at a central laboratory. Laboratory parameters and special laboratory evaluations that will be measured are listed in Table 7.

Table 7. Laboratory Analytes and Special Laboratory Evaluations

Hematology or CBC	Clinical Chemistry	Urinalysis (automated)	Special Diagnostic Tests	Hemolysis Panel
Hematocrit	Sodium	Color	HbA1c	Free plasma hemoglobin
Hemoglobin	Potassium	pH	CD4+	Haptoglobin
RBC count	Chloride	Specific gravity	Lymphocytes	Total bilirubin
WBC count	Calcium	Protein	α -fetoprotein	Conjugate bilirubin
Differential WBC count	Phosphorus	Glucose	C-reactive protein (CRP)	CBC
o Neutrophils	Serum iron	Ketones	IgG	LDH
o Lymphocytes	Bicarbonate	RBC, WBC, casts *	IgM	Urinalysis
o Monocytes	Glucose	Nitrites	Qualitative Direct Coombs test	
o Eosinophils	BUN	Bilirubin	Cortisol	
o Basophils	Creatinine	Hemoglobin		
Platelets	Total bilirubin	Urobilinogen		
MCV	Albumin			
MCH	Total protein			
MCHC	AST (SGOT)			
RDW	ALT (SGPT)			
	Alkaline phosphatase			
	LDH			
	CPK			
	Triglycerides			
	Total cholesterol			
	HDL cholesterol			
	LDL cholesterol			

* Reflex microscopic analysis to be performed only if other analytes are abnormal on automated testing

Data listings will be presented in two ways:

- Subject Profile: all laboratory data for a subject on a page.
- General Lab listing presented by Visit and Laboratory parameter

Data for each parameter of a continuous nature will be summarized by treatment period using the summary statistics for continuous data. The change from baseline to each visit will be calculated

and summarized. Data for each parameter of a categorical nature will be summarized descriptively using count and percentages for parameters with categorical results. The described summarization will be performed by visit according to treatment received during the treatment period.

Shift tables will be provided for all values and separately for abnormal values (both clinically significant abnormalities and not).

Summaries will be repeated to reflect the use of Baseline 1 and Baseline 2, as defined in [Section 5.4.2](#).

An abnormal lab listing will be produced by using clinical significance flags.

Shift tables will also be created for the EDS-EP Complete Blood Count local laboratory parameters collected at the time of EDS-EP infusions, in a manner similar to shift tables created for the standard, central laboratory evaluations. Since local labs are collected with different units, only shift tables can be created with each value classified low, normal, or high relative to the local normal range.

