A physical examination, vital signs and routine laboratory tests were performed at each monthly visit. The primary efficacy measure (ICARS) was assessed at one month, and at the 3-month visit, all efficacy assessments were done, along with the special laboratory tests (before drug infusion). A final evaluation was performed at 6 months after the initial infusion (one month after the last dose), during which all efficacy and safety assessments were performed. The occurrence of any AEs and the use of concomitant medication were recorded from the time of signing of the consent form until the end of the study. Blood samples for the PK analysis were collected from selected patients prior to dosing (0 hr), and at 4 hours and 15 and 30 days post-dose for the first and fourth infusions.

Version 1.0, 09May2015; Version 2.1, 16Nov2015; Version 3.0 (Amend. 1), 01Feb2016; Version 3.1 (Amend. 2), 28Apr2016; Version 3.2 (Amend. 3), 25May2016; Version 4.0 (Amend. 4), 29Nov2016; Version 5.0 (Amend. 5, Site-specific), 20Sep2017; Version 6.0 (Amend. 6), 29Sep2017; Version 7.1 (Amend. 7.1), Final 13 March 2018, Version 8.0 (Amend. 8.0), Final 23 April 2018; Version 10.0 (Amend. 10), Final 16 April 2019; Version 11.0 (Amend. 11), Final 24 Jun 2020

Disposition

A total of 26 patients with AT were screened and 22 were enrolled in the study, representing the ITT population. Four subjects discontinued prematurely; one withdrew consent, another patient was dropped due to a protocol violation (CD4+ lymphocytes below cut-off at baseline), and 2 patients experienced laboratory abnormalities (decrease in CD4+ lymphocytes count) that led to their withdrawal.

Demographics and Disease Characteristics

The mean (SD) age of the AT patients was 11.2 (3.5) years, with 11 (50%) patients being males. All patients were Caucasian with a mean weight of 29.1 (9.5) kg and BMI of 15.6 (2.6). The average age of diagnosis of AT was 60.0 (35.2) months, with a mean age of symptom onset of 25.9 (17.5) months. The mean baseline scores for the ICARS and VABS were 50.6 (12.8) and 5.5 (2.0), respectively. Mean baseline scores on the sub-scales of the ICARS were as follows: posture/gait disturbance – 20.9 (7.1); kinetic function – 23.1 (6.2); speech disorders – 3.5 (1.4); and oculomotor disorders – 3.2 (1.0). Two patients were on inhalational steroids at screening, and these medications were discontinued.

Efficacy Results

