- **Group 1 - Active Drug Arm:** 5 mL of dexamethasone sodium phosphate (DSP) solution (25 mg/mL) mixed with 11 mL of water for injection is added to the concentrated RBCs.
- **Group 2 - Sham Arm:** 5 mL of Hypotonic Solution 2 (sham of the 5 mL of Drug) plus 11 mL of Water for injection is added to the concentrated RBCs.

All subjects received the study treatment and completed the 49-day follow-up period.

Results

The study has been completed in the field, and the final results are summarized below.

RBC Recovery and Survival

The results for the mean RBC recovery for Group 1 (77.9%) indicate that DSP-loaded EDS-processed cells met the FDA criteria for 24-hour RBC recovery $\geq 75\%$ (Dumont and AuBuchon, 2008). The mean life span (MLS) of EDS-processed RBCs in Group 1 was 84.3 days with a mean T50 ($\alpha/2$) of 42.1 days, while these values were 88.9 days and 44.4 days, respectively, in Group 2. These data suggest that there is no adverse impact on the survival of EDS-processed cells based on a comparison with published results for RBCs used for transfusion.

In vitro characteristics of EDS-processed RBCs

Results suggest that RBCs maintain normal ATP-dependent metabolic and biochemical functions after completion of the EDS process. The alterations induced by the EDS process in the characteristics of the RBCs, e.g. MCV, total hemoglobin, hematocrit, MCHC, MCH, platelets and WBC count, do not impact their recovery and survival in the circulation. The quantity of EDS-processed RBCs (roughly 10 mL) that are infused with the EDS-EP constitutes less than 1% of the total RBCs in circulation; therefore, changes in these cells do not have an impact on the vital functions of the blood. The only purpose of this small fraction of EDS-processed RBCs is to transport DSP (and not to carry oxygen, as is the function of RBCs for transfusion) and release it into the circulation over 30 days.

Summary of Safety Data

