At Baseline (Day 0/1), vital signs and physical and neurological examinations will be repeated and the Columbia-Suicide Severity Rating Scale (C-SSRS) will be performed. The inclusion/exclusion criteria will be reviewed and patients meeting all criteria will be randomized to one of the 3 treatment groups. Two ratings will be done on the ICARS, one 24 hours before baseline (Day 0) and the other on Day 1 (pre-dose); video recording will be required for both assessments. In addition, the baseline ratings of the following efficacy measures will be performed prior to dosing: CGI-S (assess baseline severity of the patient for use in evaluating change at post-baseline visits), VABS, and EQ-5D-5L. The diverted blood sample (see [Section 11.6](#), at least 15 mL, will be drawn prior to dosing to measure baseline values for the foreseen laboratory tests. The serum and urine pregnancy test will be repeated for women of childbearing potential. A baseline measurement of bone mineral density (BMD) will be performed.

Initial Treatment Period (6 months)

CCI

To maintain the blind, all properly prepared RBCs (EDS or Placebo) will be administered to the patients, without knowledge of the actual dose or treatment being administered.

CCI

On Day 1, a blood sample will be collected for measurement of free plasma hemoglobin, 1 hr post-infusion. On Days 2 and 15, a complete hemolysis panel [free plasma hemoglobin, haptoglobin, bilirubin (total and conjugated), CBC, LDH, urinalysis] will be performed.

At Months 1, 2, 3, 4 and 5, a blood sample will be taken for dexamethasone PK before and 1 hr after the infusion (except for Month 1). Measurement of body weight and height in triplicate, as well as a C-SSRS assessment, will be performed at each of these visits. The diverted blood sample (see [Section 11.6](#)) will be collected for measurement of serum creatinine at Months 1, 2, 4 and 5, whereas creatinine will be part of the routine laboratory tests at Months 3 and 6. Upon completion of the EDS process, 2.5 mL of the treated blood will be collected for measurement of DSP concentration and a CBC. At Month 3, in selected centers, a 5-mL sample will be taken from the EryKit_01 bowl at the end of the process to assess RBC osmotic resistance.

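### Two descriptive SAP safety outputs use limits that fit the measurement poorly: a local normal range for the infusion product's blood count, and one set of vital-sign cut-offs for all ages from 6 years

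*SAP*

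**What the plan says.** **Blood count of the infusion product.** SAP 5.4.6 plans shift tables for the "EDS-EP Complete Blood Count local laboratory parameters collected at the time of EDS-EP infusions", built like those for the patients' laboratory data, with "each value classified low, normal, or high relative to the local normal range". Its stated reason for using shift tables only is that local laboratories report in different units. SAP 6.3.3 lists ten such Safety Population tables, 14.3.8.1.1 to 14.3.8.2.5.

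The specimen is the processed product. Protocol 11.2 says that after the EDS process "2.5 mL of the treated blood will be collected for measurement of DSP concentration and a CBC". Footnote u to the schedule in Protocol 11.3 says a sample from the satellite bag or another EDS-EP sampling point "will be used for determination of DSP content and CBC". Protocol 7.1.3.3 refers to "The alterations induced by the EDS process in the characteristics of the RBCs, e.g. MCV, total hemoglobin, hematocrit, MCHC, MCH, platelets and WBC count". Patients' own haematology is handled separately: "Hematology, clinical chemistry, and urinalysis will be performed at a central laboratory" (SAP 5.4.6).

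**Vital signs.** SAP 5.4.3 states: "The number and percentage of subjects at each visit with the abnormalities in Table 6 will be summarized". Table 6 has no age bands. The high flags are systolic at least 180 mmHg with a rise of at least 20, and diastolic at least 105 mmHg with a rise of at least 15. The weight flag is a change of at least 7%. The trial is open from age 6 years and above 15 kg, with no upper age limit (Protocol 9.2.1). The same SAP section also plans summaries of absolute values and of change from baseline at each visit, without cut-offs.

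**The concern.** A reference range makes a count of abnormal values meaningful only if it belongs to what was measured. A range meant for circulating blood does not describe red cells that have been processed, and nothing in either document sets a range for the product. A shift from baseline here also compares separately prepared batches, while the layout reads like the course of a patient.

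Table 6 has a related problem. A high blood-pressure limit far above a child's usual value hardly ever triggers. A flat percentage for weight triggers on growth. SAP 5.4.1 lists weight gain among potentially steroid-related events, so this is a signal the plan itself wants to see. At stake is whether these categorical safety tables can be read as intended.

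**Working it through.** The plan states no figure on this point to reproduce. The check sets the sections side by side and applies Table 6's own rules.

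**1. Product blood count**
- Specimen: processed product (Protocol 11.2; 11.3 footnote u).
- Effect of processing: MCV, total hemoglobin, hematocrit, MCHC, MCH, platelets and WBC are named as altered (Protocol 7.1.3.3). No sizes are given.
- Yardstick: the local normal range (SAP 5.4.6). No product range is defined, and the SAP does not say whose range the local one is.
- Consequence: a low or high cell may reflect processing. A parameter that is low at every infusion goes from low to low, so it shows no shift and hides variation between batches.
- Volume: 12 scheduled infusions × 175 patients = 2,100 samples at most. This is a ceiling on the number of samples, not a measure of error. Without product values, the share out of range cannot be computed.

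**2. High systolic flag**
- Assumed, not in the documents: a child's baseline of 95 to 115 mmHg.
- Rise needed to reach 180: 180 − 115 = 65; 180 − 95 = 85 mmHg.
- Normal-model simulation with 1,000,000 draws, assuming a between-patient SD of 9 and a visit-to-visit change SD of 10:

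| Assumed mean systolic | True rise 30 mmHg: flagged | True rise 40 mmHg: flagged |
|---|---|---|
| 95 | 0.002% | 0.04% |
| 110 | 0.14% | 1.3% |
| 120 | 1.3% | 6.8% |

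- Hand check at mean 110 and rise 30: SD at follow-up = √(81 + 100) = 13.45; z = (180 − 140)/13.45 = 2.97; upper tail about 0.15%. This agrees with the simulated 0.14%.
- The low systolic flag (at most 90 mmHg with a fall of at least 20) behaves differently. For means of 95 to 110 it picks up 38% to 49% of patients with a true 20 mmHg fall, and 1.5% to 2.2% with no true change.

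**3. Weight flag**
- Guide weight: the Phase II patients, "with a mean weight of 29.1 (9.5) kg" (Protocol 7.1.3.1).
- Threshold: 0.07 × 29.1 = 2.04 kg.
- Assumed growth of 2 to 3.5 kg a year, not in the documents. Month 6: 1.0/29.1 = 3.4% to 1.75/29.1 = 6.0%. Month 12: 2/29.1 = 6.9% to 3.5/29.1 = 12.0%.
- The Month 6 averages lie below 7%, but individuals vary. With an assumed SD of percent change of 3 to 5, the share flagged is 1 − Φ((7 − mean)/SD). Mean gains of 3% to 5% (roughly 2 to 3 kg a year at Month 6) give about 9% to 35%. Mean gains of 7% to 10% (roughly the same growth at Month 12) give 50% to 84%.

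**4. Descriptions that do not agree**
- Table 6 labels pulse as sitting; the text above it has pulse measured supine.
- SAP 5.4.3 mentions height at Screening; Protocol 13.2 has it in triplicate at Screening and every later visit, and footnote x has height and weight in triplicate at each monthly visit.
- Protocol 13.2 refers to Appendix 4 for clinically notable vital signs. That appendix was not available, so Table 6 could not be compared with it.

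**The case against.** The strongest reply is that little is lost. Vital-sign values and changes are summarised at every visit without cut-offs, weight gain is also tabulated as an adverse event, and patients' haematology has its own central-laboratory tables. Randomised arms grow alike, so excess gain on a steroid would still raise the percentage in that arm. At Month 6, the end of the full placebo comparison, average growth is below 7%. Every product table carries EDS-EP in its title. SAP 5.4 plans no statistical comparison of safety data between groups. All of this stands, and it limits the point to how the categorical tables read.

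It does not remove the point. A background of growth-driven flags dilutes a drug effect even when it is equal across arms. The second baseline used after a placebo switch does not cure this: at Visit 15, Month 6 switchers are measured over about 6 months of growth and Month 9 switchers over about 3, against 12 for the original active arms. A title naming EDS-EP tells the reader what was sampled, but gives no suitable range.

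A reader might go further and infer one of the following, which the documents do not support:
- *True abnormalities cannot appear.* They can, in the continuous summaries, the central haematology tables and the low-pressure flags.
- *The high-pressure category will be empty in every arm, or neither flag can separate drug from placebo.* The baseline pressures are assumed, there is no upper age limit, and the weight flag is diluted but not uninformative.
- *The local range is stated to be a patient range.* That is a strong inference; the SAP does not say whose it is.
- *The SAP names raised blood pressure as a steroid effect.* Its list has weight gain but no blood-pressure item.

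**Conclusion.** The point holds in limited form. The product blood count is judged against a local normal range although the protocol says processing changes those parameters. The resulting abnormal and shift counts cannot be read clearly, and the size of the effect is unknown. Table 6's high blood-pressure flags would rarely mark a child, and its weight flag mixes growth with drug effect, modestly at Month 6 and heavily by Month 12.

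The blood-pressure and growth figures rest on the assumed baselines, SDs and growth rates above, and on the Phase II mean weight as a guide to this population. These outputs are descriptive. The signals are weakened in one type of table, not lost from the report, and the primary analysis is unaffected. The change is worth making because it is cheap.

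**What to change.** **Product blood count.** Take tables 14.3.8.1.1 to 14.3.8.2.5 out of the patient laboratory shift tables. Convert results to common units and summarise the EDS-EP blood count per infusion by arm, labelled as a product attribute.

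**Table 6.** For patients within the age range of a standard reference, replace the absolute high blood-pressure limits with categories standardised for sex, age and height. Replace the 7% rule with change in weight-for-age or BMI-for-age z-score, using the height and weight already taken monthly. SAP 5.4.7 already uses z-scores for bone density. Keep fixed limits for adults. Also tabulate the rise of 20 mmHg systolic or 15 mmHg diastolic on its own. Protocol 7.3 notes that children with AT may weigh less than age-matched controls, so report change in z-score and not its level.

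**Reconcile** the sitting label with the supine measurement, the SAP's height schedule with Protocol 13.2, and Table 6 with Protocol Appendix 4.

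**Cost.** SAP text, revised table shells, unit conversion, an external growth and blood-pressure reference look-up, and a separate rule for adults. No new data.
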